**Aim 2:**

To maximize the utility of data collected, a mixed model analysis of variance will be utilized to determine differences between groups (between factor), differences over time (within factor), and time X group interactions.

Outcome variables of interest include 1) reductions in area of pain, 2) reductions in pain intensity and unpleasantness, 3) reductions in pain-related disability

Control variables include: 1) Improvements in tactile discrimination thresholds, 2) data from psychological questionnaires. These variables may be added as covariates to the overall model, or may be used to perform a manipulation check. JMP or R software will be used to perform analyses

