## **3 STUDY DESIGN**

Prior to commencing this investigation we will optimize the tactile discrimination threshold testing (i.e. as per baseline visit, below), and the training conditions, in up to ten participants (patients and/or healthy controls). This will serve as a pilot to refine operational aspects of study procedures before we commence the main investigation proposed herein. Following this, youth with either chronic pain (ages 10-17, n=40) or healthy youth (ages 10-17, n=20) will undergo assessments of two-point and single-point discrimination thresholds in an initial session (Aim 1). After this initial session, youth with chronic pain will participate in up to 9 additional sessions of attentional training (Aim 2). These chronic pain patients will be randomized to either two-point discrimination training (n=20) or a single-point spatially-directed attentional control condition (n=20). Participants will not be informed of which intervention they will receive (single-blind study). Psychological questionnaires will be completed in the first and last sessions in order to determine how these variables relate to tactile discrimination and response to training.

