### **6.5 Psychological Assessment/Questionnaires**

Variation in psychological states can contribute substantially to the construction of the experience of pain, and may importantly influence attentional processes related to pain. Thus, participants will undergo extensive psychological characterization with a particular focus on variables known to influence pain. Many scales will be useful for enabling comparisons of these patients with chronic pain patients in other studies, and are part of our standard testing battery.

Anxiety: The PROMIS Anxiety pediatric scales will be used to assess anxiety. The SCARED anxiety scale will be used to further characterize anxiety.

Mood and Affect: The PROMIS Depression pediatric scales will be used to assess depression. The Positive and Negative Affect Schedule - Expanded will be used to characterize mood and affect.

Mindfulness: The Freiburg Mindfulness Inventory will be used to assess mindfulness.

Impulsivity: The Barratt Impulsiveness Scale will be used to assess impulsivity.

Handedness: The Edinburgh Handedness Inventory will be used to assess the degree of handedness and will be critical in the interpretation of differences in the lateralization of nociceptive processing.

Sleep: Sleep deprivation may substantially alter pain sensitivity. The Epworth Sleepiness Scale will be used to quantify the level of daytime sleepiness, while the Pittsburgh Sleep Quality Index will be used to assess sleep quality.

Pain Interference, Disability, and Catastrophizing: The PROMIS Pain Interference Scale (pediatric version) will be used to assess how much pain interferes with daily living. Pediatric versions of the pain catastrophizing scale will be used to assess pain-related catastrophizing, while the Functional Disability Index will be used to characterize disability.

Social Status and Discrimination: Insurance, income, education level, and experience of discrimination will be used to quantify socio-economic variables.

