### 7.1 Baseline + Intervention - Visit 1 (up to 3 hours)

- Completion of informed consent/assent prior to initiation of study procedures
- Obtain information for payment, provide ClinCard
- Randomize to intervention
- Review medical history
- Document all concomitant medications including prescribed, over the counter, and nutraceutical supplements
- Administer questionnaires
- Assess pain intensity, unpleasantness, qualitative aspects of pain
- Assess spatial extent of pain (body map or patient's own photo)
- Demonstration of two-point/single-point discrimination procedure
- Assess two-point/single-point discrimination
- Initiate intervention (TPD training or Control)
- Assess pain intensity, unpleasantness
- Assess spatial extent of pain

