**7.3. Intervention+Completion - Visit 10 (up to 3 hours)**

Assess pain intensity, unpleasantness, qualitative aspects of pain  
Assess spatial extent of pain  
Final intervention (TPD training or Control)  
Assess two-point/single-point discrimination  
Assess pain intensity, unpleasantness, qualitative aspects of pain  
Assess spatial extent of pain  
Administer psychological questionnaires

Note that some of the procedures above may be omitted for the purpose of streamlining the study visits, or if procedures are deemed to be incongruent with the participants' ongoing clinical treatments. Omitting these procedures would reduce participant burden and would have no impact on safety.

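### Section 9.1 allows improvement in discrimination thresholds, a post-training variable and the hypothesised mechanism, as a covariate in the Aim 2 efficacy model

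*Protocol*

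**What the plan says.** Protocol section 9.1 analyses Aim 2 with a mixed-model analysis of variance containing group, time and time x group. The outcomes are worded as reductions: in area of pain, in intensity and unpleasantness, and "3) reductions in pain-related disability". It then lists two kinds of control variable: "Improvements in tactile discrimination thresholds, 2) data from psychological questionnaires. These variables may be added as covariates to the overall model". The full sentence on their use reads: "These variables may be added as covariates to the overall model, or may be used to perform a manipulation check".

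The timing comes from section 7. At Visit 1 (7.1), discrimination is assessed before the entry "Initiate intervention (TPD training or Control". At the final visit (7.3), the entry "Assess two-point/single-point discrimination" follows the last training session, and "Administer psychological questionnaires" comes at the end of the same visit.

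Section 3 says the questionnaires are "completed in the first and last sessions in order to determine how these variables relate to tactile discrimination and response to training". Section 6.5 places a disability measure in the questionnaire battery: "the Functional Disability Index will be used to characterize disability".

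Section 1 gives the rationale: discrimination training may retune spatial somatosensory processing and so reduce widespread pain.

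**The concern.** A covariate in an efficacy model should not itself be affected by treatment. Threshold improvement is a difference between a value taken before training and one taken after it, so it cannot be a baseline variable on any reading. It is also what the training is meant to change. A model that holds it fixed asks whether two-point training helps beyond its effect on discrimination. Aim 2 asks whether it helps at all.

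Two things are at stake if the option is taken. The group effect loses whatever share acts through improved discrimination, so an effective treatment could look weak or null. And because threshold change is not randomised, anything that drives both threshold change and pain can introduce bias, even where training has no effect on pain.

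A secondary point concerns the questionnaires. Section 9.1 does not limit them to the first session, so last-session scores are not excluded. That includes the disability score when disability is the outcome.

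**Working it through.** **The plan's own figure.** There is none to reproduce. Section 9.2 sets 20 per group by heuristic and gives no effect size, SD or power. Every effect size below is an assumption chosen for illustration.

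**Inputs.** 20 per arm (section 9.2). Assumed: total training effect tau = -0.9 (negative favours two-point training), in units of the within-arm SD of a subject's true change over the course; arm separation on threshold improvement s = 0.5 to 1 SD; mediated share m from 25% to 100%.

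**1. Outcome analysed as change from Visit 1.** Let A be arm (1 = two-point training), M threshold improvement and Y the change in outcome:

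- M = s·A + noise
- Y = c·A + b·M + noise
- Group effect without M: tau = c + b·s
- Group effect with M as covariate: c = tau·(1 - m), where m = b·s/tau

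With tau = -0.90 and s = 1:

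| Mediated share | Without M | With M, by formula | With M, simulated (8,000 runs) |
|---|---|---|---|
| 25% | -0.90 | -0.90 × 0.75 = -0.675 | -0.678 |
| 50% | -0.90 | -0.90 × 0.50 = -0.45 | -0.448 |
| 75% | -0.90 | -0.90 × 0.25 = -0.225 | -0.226 |
| 100% | -0.90 | 0 | 0.000 |

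A separate simulation of a change score (10,000 runs, total effect 0.8 with positive favouring training, s = 1) gave 0.79 falling to 0.39 at half mediation, and 0.80 falling to 0.00 at full mediation.

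The amount lost is b·s. It shrinks if little of the effect runs through threshold change, and also if the arms separate little. With b = -0.45 it is 0.45 at s = 1, 0.225 at s = 0.5 and nothing at s = 0.

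**2. Shared causes, no true effect on pain.** If threshold improvement and pain reduction correlate rho within arm, and both have unit SD, the adjusted group effect is rho·s instead of 0, against training:

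- s = 0.5: 0.3 × 0.5 = 0.15 and 0.5 × 0.5 = 0.25 (simulated 0.153 and 0.249; rejection 7% and 9%)
- s = 1: 0.3 × 1 = 0.30 and 0.5 × 1 = 0.50 (simulated 0.307 and 0.497; rejection 11% and 23%)

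The nominal rate is 5%.

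**3. Outcome analysed as repeated measures.** Here the form of the covariate decides. Time x group from REML mixed models (first and last session, random intercept, 120 runs, tau = -0.9, s = 1):

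| Form of covariate | 50% mediated | 100% mediated |
|---|---|---|
| None | -0.936 | -0.927 |
| Subject-level main effect | -0.936 | -0.927 |
| Threshold as time-varying covariate | -0.651 | -0.186 |
| Covariate by time | -0.469 | -0.010 |

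A covariate that is constant within subject cancels from the within-subject contrast, so the second row equals the first. It does alter the group main effect, which goes from -0.45 to about -0.22 at 50% and to about 0 at 100%. The unadjusted value is only -0.45 because the main effect averages over visits from no training to full training (-0.9 × 0.5).

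**4. Questionnaires.** Sections 3 and 7.3 show that last-session scores exist; section 6.5 puts the disability scale in the battery; section 9.1 makes disability an outcome. Nothing in 9.1 rules out a last-session score as covariate, but nothing names one either.

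**The case against.** The strongest reply is that the use is optional, and that the sentence permitting it also offers a sound alternative, the manipulation check. The model with group, time and time x group is stated first, without covariates. This stands: the problem arises only if the option is taken. It does not dispose of the point, because one of the two permitted uses is unsound and the protocol names no unadjusted or baseline-only model as the main analysis. A separate statistical analysis plan may narrow the choice, but this is an express permission in section 9.1, not a detail left for later.

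A second reply is that the usual test of training in this design is time x group, which a subject-level main-effect covariate leaves untouched. This also stands. A reader might infer that any use of the covariate distorts the training contrast, or that it turns a group main effect which was the total effect into something else. Neither follows. In a repeated-measures model the group main effect was never the total effect, and damage to time x group needs a covariate-by-time term or a time-varying covariate, which section 9.1 does not name. The point keeps its force because the outcomes are worded as reductions. If they are analysed as change from Visit 1, the group term is the training effect, and even a plain covariate removes its mediated part.

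Third, a reader might infer that adjusting the disability outcome for last-session disability would reverse the sign of its effect. The algebra is right for the repeated-measures group main effect: with two sessions of equal variance and correlation r, tau/2 becomes -r·tau/2. But section 9.1 does not name the disability scale as a covariate; its inclusion is inferred from its place in section 6.5. First-session scores would satisfy the wording and be unobjectionable. Timing is left open here, not stated wrongly, so this is secondary.

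Finally, every magnitude is assumed. Both arms receive discrimination training with immediate feedback (sections 5.1 and 5.2), so separation on threshold improvement could be small, and the distortion with it.

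**Conclusion.** The point holds in limited form. Section 9.1 permits a post-training variable, which is also the hypothesised mechanism, as a covariate in the Aim 2 efficacy model. If it is used when outcomes are analysed as reductions from Visit 1, or in a form that interacts with or varies over time, the group effect loses its mediated share in whole or in part and can be biased by shared causes. Used as a subject-level main effect in a repeated-measures model, it changes only the group main effect.

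The size cannot be derived from the protocol. The drop from -0.90 to -0.45 or to 0 illustrates the mechanism under an assumed 1 SD separation and 50% or 100% mediation; it is not a prediction. The direction of the loss follows from the design whenever part of the effect is mediated.

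Section 9.2 says the study will determine effect size, and a reader might infer that a future trial would be planned on a distorted estimate. The protocol does not say the adjusted model will supply that estimate, so no sample-size consequence is claimed.

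**What to change.** In section 9.1, remove threshold improvement from the covariates that may enter the Aim 2 efficacy model. Limit any covariates in that model to values measured at Visit 1 before training starts; for questionnaires this means first-session scores. Keep threshold change for the manipulation check already planned, or for a separate mediation analysis labelled exploratory.

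The cost is a change of wording. The Visit 1 thresholds and first-session questionnaire scores are already scheduled, so no new data, visits or participants are needed.

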## **9.2 Number of Participants to be Enrolled**

This is the first investigation of an entirely novel question, and will be used to determine both effect size and variability. Thus, we will apply a heuristic approach based on prior experience obtained within-subjects variability in pain ratings in studies of spatial aspects in acute experimental pain in healthy adults (Quevedo and Coghill, 2007; Quevedo et al., 2017). With these studies, we have obtained reproducible results from 15 subjects in within subjects designs. Thus, we have selected N=20 per group to compensate for the reduced power of the between subjects design. Up to 10 additional participants will serve to optimize operational aspects of study procedures as potential pilot subjects.

## **9.3 Level of Significance**

Statistical significance will be defined by  $p<0.05$ .

## **9.4 Participants to be Included in Analyses**

All participants without excessive missing data (i.e. completion of <5 sessions) will be included in analyses.

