## 7 Study Visits

The duration of two-point discrimination needed to improve pain remains completely unknown. To optimize retention, we may truncate the number of visits, depending on subject availability, with procedures in Visit 10 being performed at the final visit. Healthy control participants will only participate in the baseline visit.

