### 7.2 Intervention - Visits 2-9 (1 hour)

- Determine any changes in medications or concurrent conditions
- Assess pain intensity, unpleasantness, qualitative aspects of pain

Assess spatial extent of pain  
Continue intervention (TPD training or Control)  
Assess pain intensity, unpleasantness, qualitative aspects of pain  
Assess spatial extent of pain

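### The single session-count rule in section 9.4 makes the Aim 2 analysis set depend on attendance after randomisation and applies the wrong criterion to Aim 1

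*Protocol*

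**What the plan says.** Protocol section 9.4 is the only statement of who is analysed: "All participants without excessive missing data (i.e. completion of <5 sessions) will be included in analyses". It does not separate the aims, and no other section restricts it or defines a set of all randomised patients.

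The rule has to be read with four other places:

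- **Section 7.1 (Visit 1)** lists "Randomize to intervention", and training starts at that same visit. Sections 7.2 and 7.3 continue it to Visit 10.
- **Section 7** says that "we may truncate the number of visits, depending on subject availability, with procedures in Visit 10 being performed at the final visit". No minimum number of visits is given. It also says of the other cohort: "Healthy control participants will only participate in the baseline visit".
- **Section 3 and section 9.1 (Aim 1)** take the Aim 1 thresholds from the initial session and compare patients with healthy controls.
- **Section 9.1 (Aim 2)** plans a mixed model with a between-arm factor and "differences over time (within factor), and time X group interactions".

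**The concern.** For Aim 2, the number of sessions a patient completes is known only after allocation and after training has begun. Selecting on it gives up the protection of randomisation. If attendance is related to response, and related differently in the two arms, the time-by-group comparison is biased in favour of the arm that loses its poorer responders. Equal exclusion rates are no safeguard unless the reasons for stopping are also the same in both arms.

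The rule also fits badly with section 7. A patient whose visits are shortened as that section allows can supply first-visit and final-visit outcomes and still be classed as having too much missing data. The two sections can both be followed, but together they discard recorded follow-up.

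For Aim 1, session count says nothing about whether the baseline thresholds are complete. A patient with full baseline data who later stops attending would be lost from a baseline comparison for no analytic reason.

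Section 9.2 says the study is meant to supply an effect size and its variability, so an estimate restricted to attenders could carry into later planning.

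**Working it through.** There is no figure in the plan to reproduce. The 20 per group in section 9.2 is heuristic, with no effect size, SD, power or dropout rate.

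**1. The rule set against each aim**

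| | Aim 1 | Aim 2 |
|---|---|---|
| Data needed | thresholds at the first session | repeated pain outcomes and disability |
| Sessions planned | controls 1; patients' first session only | up to 10 |
| Effect of requiring 5 sessions | drops patients with complete data; read literally, all controls (1 < 5) | set fixed by attendance after randomisation |

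The literal loss of the controls is a slip in wording. Nothing below rests on it.

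**2. Data set aside for a patient truncated to 4 visits**

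Sections 7.1 to 7.3 assess pain intensity, unpleasantness and spatial extent before and after training at each visit: 2 × 4 = 8 assessments of each. This is an upper limit, since section 7.3 notes that "some of the procedures above may be omitted for the purpose of streamlining the study visits". Questionnaires, including the disability measure, are planned for the first and last sessions only (section 3). Such a patient can therefore have both planned disability scores and still be excluded.

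**3. Aim 1 precision**

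The detectable standardised difference is approximately (1.960 + 0.842) × √(1/n₁ + 1/n₂), for two-sided 0.05 (sidedness assumed) and 80% power. The exact value uses the noncentral t. A simple two-group t-test is assumed, with 20 controls and excluded patients not replaced.

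| Patients / controls | Approximate | Noncentral t |
|---|---|---|
| 40 / 20 | 2.802 × 0.274 = 0.77 | 0.780 |
| 36 / 20 (10% lost) | 2.802 × 0.279 = 0.78 | 0.796 |
| 32 / 20 (20% lost) | 2.802 × 0.285 = 0.80 | 0.814 |

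Section 6.1 allows up to 50 patients but does not say that excluded patients are replaced.

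**4. Aim 2 bias (illustrative; attendance and variances are assumed)**

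- From the protocol: 20 per arm, 10 visits, time-by-group mixed model, significance level 0.05.
- Assumed: no true effect; random intercept SD 0.8; random slope SD 0.8 over visits 1 to 10; stoppers have visits 1 to 4 only, so section 9.4 removes them.
- Case A: residual SD 0.5, with the stopping score correlated 0.7 with observed change over visits 1 to 4. Case B: residual SD 0.3, correlation 1.0.
- REML fit with random intercept and slope; t-test on patients minus 2 degrees of freedom; 4,000 runs per case.

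Entries are absolute bias in SD of true change / type I error. Monte Carlo error is about 0.006 SD and 0.35 percentage points.

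| Stopping (arm 1 vs arm 2) | Case | 9.4 set | All randomised |
|---|---|---|---|
| None | A | 0.006 / 4.4% | same set |
| | B | 0.003 / 4.4% | same set |
| Baseline level, 30% vs 10% | A | 0.001 / 5.0% | 0.003 / 5.6% |
| | B | 0.000 / 5.4% | 0.019 / 5.4% |
| Response, 20% in both | A | 0.002 / 5.0% | 0.005 / 5.4% |
| | B | 0.005 / 5.4% | 0.007 / 5.5% |
| Response, 30% vs 10% | A | 0.099 / 5.3% | 0.010 / 5.0% |
| | B | 0.175 / 7.5% | 0.015 / 5.1% |
| Response 10% vs random 10% | A | 0.052 / 6.0% | 0.016 / 5.7% |
| | B | 0.108 / 6.9% | 0.015 / 5.6% |
| Response 20% vs random 20% | A | 0.117 / 5.7% | 0.006 / 4.9% |
| | B | 0.214 / 8.8% | 0.008 / 5.1% |
| Unrecorded slope 20% vs random 20% | A | 0.348 / 14.0% | 0.272 / 10.7% |
| | B | 0.347 / 16.5% | 0.210 / 9.3% |

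Keeping everyone brings no gain in Aim 2 precision. With response-driven stopping of 20% in both arms, the standard error for the 9.4 set against all randomised is 0.410 against 0.412 (A) and 0.352 against 0.366 (B).

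**The case against.** The harm cannot be shown from the documents. No attendance figures are given. Both arms train at the same sites with immediate feedback, and participants are not told their arm, so stopping that differs by arm is not the obvious expectation. Where stopping follows baseline level or works identically in both arms, the 9.4 set shows essentially no bias. In baseline-driven case B the all-randomised analysis is in fact slightly worse (0.019 against 0.000 SD). In the moderate case A, type I error under response-driven stopping rises by only 0.3 to 0.8 points over the all-randomised analysis, which is close to simulation noise. The clearest inflation needs stopping to follow observed change perfectly. The largest bias comes from stopping on an unrecorded trajectory, where the remedy leaves most of it in place.

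On Aim 1, a control with one planned visit has no missing sessions, so the natural reading confines the rule to patients. Losing a few of those barely moves precision. Section 9.4 can also be read as supplying the minimum that section 7 omits, so the two sections do not contradict each other.

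Most of this stands and limits the weight of the point. It does not rescue the rule. Participant blinding does not stop patients from acting on their own response. The bias in case A is still 0.05 to 0.12 SD when response-driven stopping differs by arm. The rule is also written into the protocol, so it is not a detail left for a later analysis plan.

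**Conclusion.** The point holds and should be fixed, although its practical size is uncertain. As written, the only stated Aim 2 set is conditional on attendance after randomisation, and the same cut-off is the wrong criterion for Aim 1.

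Whether the Aim 2 comparison is actually biased, and in which direction, cannot be determined from the protocol. Under the assumed variances and stopping rates, the bias from section 9.4 is about zero with baseline-driven or identical stopping. It is 0.05 to 0.21 SD of true change, with type I error of 5.3 to 8.8%, when response-driven stopping differs between arms. Analysing all randomised patients reduces that to 0.01 to 0.02 SD and 4.9 to 5.7%. If stopping follows a trajectory the visits do not capture, bias falls from about 0.35 to between 0.21 and 0.27 SD but does not disappear.

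The Aim 1 cost is small: the detectable difference moves from 0.78 to 0.80 or 0.81 SD if 10% or 20% of patients are lost. Apart from any bias, usable baseline and follow-up data would be thrown away.

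**What to change.** Rewrite section 9.4 separately for each aim.

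- **Aim 1:** include every participant with baseline discrimination data, whatever the number of sessions attended. This also removes the wording slip over the controls.
- **Aim 2:** include every randomised patient in the allocated arm, using all available assessments in a likelihood-based mixed model. Keep the set with at least five sessions as a sensitivity analysis.
- Report the number of patients below five sessions in each arm.

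The cost is wording only, with no added patients or visits, and the sponsor's intended analysis survives as the sensitivity analysis. There are two drawbacks. The Aim 2 estimate will include patients with little training, so it may be slightly less favourable. The model also assumes that missing visits are explained by the observed data; where they are not, some bias remains.
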